#### **9.4.2.2 Overall survival**

OS in the FAS population will be analyzed using a stratified log-rank test, using the same methodology as described for the primary PFS endpoint. The effect of durvalumab + olaparib with durvalumab + placebo will be estimated by the HR together with its corresponding 95% CIs and from a stratified Cox model. KM plots will be presented by treatment arm. Summaries of the number

and percentage of patients who have died, those still in survival follow-up, those lost to follow-up, and those who have withdrawn consent will be provided along with the median OS for each treatment group. Subgroup analyses maybe performed if there are a sufficient number of OS events.

#### **9.4.2.3 OS18**

OS18 will be summarized (using the KM curve) with a landmark estimate from the KM curve by treatment arm.

#### **9.4.2.4 Objective response rate**

The ORR will be based on RECIST 1.1 using the Investigator tumor data. The ORR will be compared between durvalumab + olaparib and durvalumab + placebo using logistic regression models adjusting for the same factors as the primary and secondary endpoint PFS dependent on the population being analyzed. The results of the analysis will be presented in terms of an odds ratio together with its associated profile likelihood CI and p-value (based on twice the change in log-likelihood resulting from the addition of a treatment factor to the model).

Summaries will be produced that present the number and percentage of patients with a tumor response (CR/PR). Overall visit response data will be listed for all patients (ie, the FAS). For each treatment arm, best overall response (BoR) will be summarized by n (%) for each category (CR, PR, SD, PD, and NE). No formal statistical analyses are planned for BoR.

The ORR analysis described above will be repeated for a subset of patients in the FAS with HRRm.

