### 1.3 Schema

The general study design is summarized in [Figure 1](#).

**Figure 1** Study design

\*The expected prevalence of HRRm is approximately 14%.

HRR Homologous recombination repair; HRRm Homologous recombination repair mutation;  
HRRwt Homologous recombination repair wild-type; TCC Transitional cell carcinoma; UC Urothelial  
carcinoma.

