PD-L1 is expressed in a broad range of cancers. Based on these findings, an anti-PD-L1 antibody could be used therapeutically to enhance antitumor immune responses in patients with cancer. Results of nonclinical and clinical studies of monoclonal antibodies (mAbs) targeting the PD-L1/PD-1 pathway have shown evidence of clinical activity and a manageable safety profile, supporting the hypothesis that an anti-PD-L1 antibody could be used to therapeutically enhance antitumor immune response in cancer patients (Brahmer et al 2012, Hirano et al 2005; Iwai et al 2002; Okudaira et al 2009; Topalian et al 2012; Zhang et al 2008) with responses

that tend to be more pronounced in patients with tumors that express PD-L1 (Powles et al 2014, Rizvi et al 2015, Segal et al 2015). In addition, high mutational burden, for example, in bladder carcinoma (Alexandrov et al 2013), may contribute to the responses seen with immune therapy.

Immunotherapy with PD-1 (ie, PDCD1) or PD-L1 (ie, CD274) inhibitors have shown significant activity in advanced UC. Atezolizumab, a PD-L1 inhibitor, showed an ORR of 23% and median OS of 15.9 months (95% CI 10.4 to not estimable). Treatment was generally well tolerated with only 8% of patients discontinuing therapy due to an adverse event (AE) (Balar et al 2017). Nivolumab and pembrolizumab, 2 anti-PD-1 agents, and atezolizumab, an anti PD-L1 agent, have been granted approval by agencies such as the United States of America (US) Food and Drug Administration (FDA) and the European Medicines Agency (EMA) for the treatment of a number of malignancies, including metastatic melanoma, squamous and non-squamous NSCLC, squamous cell carcinoma of the head and neck, and urothelial carcinoma. Pembrolizumab showed a similar ORR of 29% as initial treatment of advanced UC in a study of 370 cisplatin-ineligible patients, including patients with Eastern Cooperative Oncology Group (ECOG) performance score of 2 (O'Donnell et al 2017). Given the observed efficacy and favorable safety profile, patients with UC ineligible for platinum-based chemotherapy have derived particular benefit from immunotherapy. Durvalumab monotherapy studies in cis-ineligible patients are ongoing.

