### 2.3.2 Durvalumab

#### 2.3.2.1 Benefits

A total of 23 sponsored clinical studies have been or are being conducted with durvalumab as a single agent or in combination with other agents. As of 12 July 2016, a total of 5225 patients had received at least 1 dose of durvalumab across a number of tumor types (refer to the current durvalumab IB).

The potential benefit of durvalumab in bladder cancer was demonstrated in a cohort of 182 patients with locally advanced or metastatic UC who had progressed while on or after a platinum-based chemotherapy. The overall ORR based on blinded independent central review (BICR) was 17%. In patients who had received only 1 neoadjuvant or adjuvant prior therapy, the ORR was 24%. With

a median follow-up time of 5.6 months, among the responding patients, 45% had ongoing responses of 6 months or longer and 16% had ongoing responses of 12 months or longer (median DoR: not reached [range: 0.9+ months to 19.9+ months]) (Massard et al 2016).

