## 9.2 Sample size determination

The study is sized to characterize the PFS benefit of durvalumab in combination with olaparib versus durvalumab monotherapy in first-line patients with unresectable Stage IV UC.

Approximately 150 patients globally will be randomized in a 1:1 ratio to either the durvalumab + olaparib treatment group or the durvalumab + placebo treatment group, 75 patients per arm. The randomization will be stratified based on HRR status (mutant versus wild type) and Bajorin risk index (0 versus 1 versus 2).

The DCO for the primary analysis of PFS will occur when approximately 118 PFS events have occurred across both treatment groups (79% maturity). Assuming a median survival of 3 months for durvalumab monotherapy and recruitment of 150 patients in 6 months, it is estimated that this DCO will occur 7 months following recruitment of the last patient.

If the true PFS hazard ratio (HR) is 0.55 (likely to correspond to an 82% prolongation of PFS), the study will have 90% power to demonstrate a statistically significant difference for PFS at the 2-sided 5% significance level.

The smallest treatment difference that could be statistically significant at the primary analysis of PFS is an HR of 0.69 (assuming a 2-sided p-value of 0.5).

There will be up to 2 analysis timepoints for OS. The first OS analysis will occur at the same time as the primary PFS analysis and will be based on an estimated 44 OS events across therapies (29% maturity), and the second OS analysis will occur when

approximately 100 OS events have occurred (67% maturity). With an approximate 6-month recruitment period and an assumed median OS of 16 months in the durvalumab + placebo arm, it is anticipated that the final analysis will be performed at approximately 27 months after the last patient has been recruited.

Assuming the true OS HR is 0.75, the study will have 30% power to demonstrate a statistically significant OS effect with a 5% 2-sided significance level, allowing for 2 analyses of the data. The smallest treatment difference at the second analysis of OS that could be statistically significant is an HR of 0.68.

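### The HRRm response-rate comparison uses a large-sample likelihood-ratio test in about 21 patients with 4-6 responders; as written, its nominal 5% test rejects about 10-13% of the time under no effect

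*Protocol*

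**What the plan says.** Section 9.4.2.4 specifies one method for ORR: logistic regression adjusted for the PFS factors as far as they apply to the population analysed. It reports an odds ratio, a profile-likelihood CI and a p-value "based on twice the change in log-likelihood resulting from the addition of a treatment factor to the model". The same section ends: "The ORR analysis described above will be repeated for a subset of patients in the FAS with HRRm". ORR in HRRm patients is a listed secondary endpoint (Section 3, Table 3).

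The size of the subset follows from two statements: "Approximately 150 patients globally will be randomized in a 1:1 ratio" (Section 9.2) and, in per cent, "The expected prevalence of HRRm is approximately 14" (Section 1.3).

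Two other provisions bear on sparse data:
- The text after Table 17 (Section 9.4.2) allows stratification levels to be merged or factors left out, before unblinding, if numbers are too small.
- Section 9.4.2.1 treats a PFS subgroup with fewer than 10 events as unsuitable for formal analysis.

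Neither sets a minimum number of responders or a small-sample method for ORR.

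**The concern.** A likelihood-ratio statistic follows its chi-square reference only in large samples. In HRRm the model has five parameters: intercept, treatment, PD-L1 and two Bajorin terms (HRR status is constant). It would be fitted to about 21 patients with about as many responders as parameters. In data that sparse the test can reject well above its nominal level. The odds ratio is not finite when one arm has no responders, or when treatment and covariates together separate responders from non-responders.

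HRRm is the subset in which Section 2.1 anticipates particular benefit, so readers will look at this result. A p-value that is too small too often, with a CI built on the same approximation, could make a chance difference of a few responders look like evidence and influence later development.

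**Working it through.** **Plan's own figure.** The protocol gives no error rate or power for ORR in HRRm. Its PFS design does reproduce: 4 × (1.960 + 1.282)² / (ln 0.55)² = 42.03 / 0.3574 = 117.6, so 118 events for 90% power, as Section 9.2 states.

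**Inputs from the protocol**
- HRRm patients: 150 × 0.14 = 21, about 10 v 11.
- First-line response rates (Section 2.2.1): for atezolizumab, "showed an ORR of 23% and median OS of 15.9 months", giving 21 × 0.23 = 4.8 responders. Also "Pembrolizumab showed a similar ORR of 29% as initial treatment of advanced UC", giving 21 × 0.29 = 6.1.
- Durvalumab after platinum (Section 2.3.2.1), in per cent: "The overall ORR based on blinded independent central review (BICR) was 17", giving 21 × 0.17 = 3.6.
- Level: two-sided 5% (95% CIs and two-sided p-values, Section 9.4).

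**Assumptions, not in the protocol.** PD-L1 high in 50% (65% also tried). Bajorin 0/1/2 split 20/60/20, 25/50/25 or 33/34/33. Either 1:1 balance or blocks of 4 within Bajorin level. The same response probability in both arms.

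**A case by hand, no covariates.** With 0/10 v 3/11 responders, the maximised log-likelihood is 3 ln(3/11) + 8 ln(8/11) = −6.446 with treatment, and 3 ln(3/21) + 18 ln(18/21) = −8.612 without. Twice the difference is 4.33, so p = 0.037 with an infinite odds ratio. Fisher's exact test gives (165 + 120)/1330 = 0.21.

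**Null rejection at nominal 5%, n = 21 (simulation; exact enumeration where no covariates)**

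| Model | Rejection rate |
|---|---|
| PD-L1 + three-level Bajorin (as written) | about 10-13% at ORR 17-29% |
| PD-L1 + Bajorin pooled to two levels | 9-10% |
| PD-L1 only | 7-9% |
| No covariates, 10 v 11 | 7.4-8.2% |
| No covariates, 9 v 12 | 4.8-5.3% |
| No covariates, 8 v 13 | about 8% |

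For the model as written, restricting to trials with exactly 4-6 responders gives about 10%. Changing the PD-L1 and Bajorin splits moved these figures little.

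**Zero or infinite treatment odds ratio, model as written.** Given 4-6 responders, about 10% (9-13% across the assumptions). Over all trials, including those with fewer responders: about 10-13% at ORR 29%, 17-20% at 23% and 30% at 17%.

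**Alternatives under the null, n = 21**
- Firth-penalised likelihood-ratio test with the same covariates: about 3-4%, and below 5% in every setting tried.
- Mid-p exact test, two-sided by ordering tables on their probability: about 3-5%.
- Fisher's exact test: about 1.5-3%.

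**Full analysis set, n = 150.** The planned adjusted test rejects about 5.5%, so the problem is confined to the HRRm repeat.

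**The case against.** Several points against the concern are fair.

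1. The protocol lets sparse factors be pooled or dropped, and three Bajorin levels in 21 patients is the obvious case. This stands: the 10-13% applies only if both factors are kept. But the clause is optional and turns on stratum sizes, not responders, and most reduced models still exceed 5%.
2. A reader might infer that the unadjusted test always runs above 5%. It does not: at 9 v 12 it is nominal. Part of the excess is discreteness that changes with the arm split, which is not known in advance.
3. A reader might infer that the odds ratio will often be infinite. About one in ten is the fair figure for the expected 4-6 responders. The 30% figure rests on a 17% response rate from patients who had progressed on or after platinum, whereas this trial is first-line. The likelihood-ratio p-value and profile interval remain defined when an arm has no responders (the interval is one-sided), and responder counts will be shown.
4. No decision hangs on this p-value. Formal testing is PFS then OS, and success is defined by PFS alone (Sections 9.1 and 9.4.10). This stands and limits the weight of the point.
5. Fisher's test misses 5% in the other direction. At 10 v 11 its power is 16% against 29% for the planned test (unadjusted; response 23% v 50%), although part of that gap is the price of removing the inflation. This is why Fisher is not the preferred remedy.
6. The SAP, not seen here, may add a small-sample fallback. Even so, the protocol itself names the likelihood-ratio analysis for this subset, so this is a stated choice and not a detail left open.

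**Conclusion.** The point holds in a limited form and merits correction. With both covariates kept, the HRRm ORR test rejects about 10-13% under no effect against a nominal 5%; with factors pooled or dropped, about 5-10%, depending on the factors kept and the arm split. The figures rest on 14% prevalence, the cited 17-29% response rates, and assumed PD-L1 and Bajorin distributions.

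It would be wrong to conclude that the trial's type I error is inflated, or that a stated error rate for this endpoint is doubled. ORR in HRRm is outside the alpha sequence, and the protocol states no error rate for it. What cannot be taken at face value is the nominal p-value and CI for that subset.

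The protocol already applies caution to sparse data elsewhere: the 10-event rule for PFS subgroups, and no formal comparison for duration of response (Section 9.4.2.5). ORR in HRRm has no such protection.

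**What to change.** In Section 9.4.2.4, for the HRRm subset only, replace the likelihood-ratio p-value and profile-likelihood CI with one of the following, chosen before unblinding:
- Firth-penalised logistic regression, with a penalised-likelihood p-value and CI. This keeps covariate adjustment and gives a finite odds ratio.
- An unadjusted mid-p exact test, with its two-sided ordering stated, and a score 95% CI for the difference in ORR.

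Fisher's exact test is valid but more conservative. Keep the planned model for the full analysis set.

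The cost is one sentence in the protocol or SAP and a few lines of standard code. The downside is somewhat lower nominal power in HRRm and, with the mid-p option, no covariate adjustment.

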#### **9.4.2.5 Duration of response**

KM estimates will be provided for the DoR in responding patients (ie, median DoR and 95% CIs) by treatment arm, including the associated KM curves (without any formal comparison of treatment arms or p-value attached).

The DoR analysis described above will be repeated for a subset of patients in the FAS with HRRm.

#### **9.4.2.6 PFS6**

PFS6 will be summarized with a landmark estimate from the KM curve by treatment arm.

#### **9.4.2.7 The PFS6 analysis described above will be repeated for a subset of patients in the FAS with HRRm.Patient-reported outcomes**

The main PRO measures identified in the secondary objectives are global health status/QoL, physical function, pain, and fatigue scales of the EORTC QLQ-C30. Compliance rates summarizing questionnaire completion at each visit will be tabulated for each questionnaire; further details will be included in the SAP.

#### **EORTC QLQ-C30**

Time to symptom deterioration in symptom, function, and HRQoL will be analyzed respectively for each of the 3 multiple-item symptom scales (fatigue, pain, and nausea/vomiting), the 5 function scales (physical, role, cognitive, emotional, and social), and global health status/QoL. These analyses will be performed for the FAS using a log-rank test stratified by the same covariates as for the primary PFS endpoint and illustrated using a KM plot by treatment arm. Summaries of the number and percentage of patients who have an event, as well as who were censored, will be provided along with the medians for each treatment.

A summary of the symptom improvement rate for each of the 3 symptom scales will be produced. Similarly, a summary of the best HRQoL/function response rate for each of the 5 function scales and global health status/QoL will be produced. The best symptom response rate and HRQoL/function response rate will be analyzed by comparing the treatment arms using a logistic regression model as described for the analysis of ORR. The odds ratio, p-value, and 95% CI will be presented graphically on a forest plot.

Summaries of absolute and change from baseline values for each of the 3 symptom scales/items, 5 individual symptom items (dyspnea, loss of appetite, insomnia, constipation, and diarrhea), 5 function scales and the global health status/QoL score, and each functional domain will be reported by visit for each treatment arm. The mean change from baseline will be analyzed for each symptom scale and function scale of interest using a mixed model for repeated measures and potentially a piecewise linear model to further support data interpretation. Full details of this and appropriate sensitivity analyses will be described in full in the SAP.

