#### **EORTC QLQ-C30**

The EORTC QLQ-C30 consists of 30 questions that can be combined to produce 5 function scales (physical, role, cognitive, emotional, and social), 3 symptom scales (fatigue, pain, and nausea/vomiting), and a global measure of health status. The EORTC QLQ-C30 will be scored according to the EORTC QLQ-C30 scoring manual ([Fayers et al 2001](#)). An outcome variable consisting of a

score from 0 to 100 will be derived for each of the symptom scales, each of the function scales, and the global health status scale in the EORTC QLQ-C30 according to the EORTC QLQ-C30 scoring manual. Higher scores on the global health status and function scales indicate better health status/function, but higher scores on symptom scales represent greater symptom severity.

Definition of clinically meaningful changes

Changes in score compared with baseline will be evaluated. A minimum clinically meaningful change is defined as an absolute change of  $\geq 10$  in the score from baseline for scales from the EORTC QLQ-C30 (Osoba et al 1998). For example, a clinically meaningful improvement in physical function (as assessed by EORTC QLQ-C30) is defined as an increase of  $\geq 10$  in the score from baseline, whereas a clinically meaningful deterioration is defined as a decrease of  $\geq 10$  in the score from baseline. At each post-baseline assessment, the change in symptoms/ functioning from baseline will be categorized as improvement, no change, or deterioration as shown in Table 16. A patient’s best overall response in symptoms, function, or global health status/QoL will be derived as the best response the patient achieved, based on evaluable PRO data collected during the study period. Additional details will be provided in the SAP.

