#### Symptom improvement rate

The symptom improvement rate will be defined as the number (%) of patients with 2 consecutive assessments at least 14 days apart that show a clinically meaningful improvement (a decrease from baseline score  $\geq 10$  for EORTC QLQ-C30 symptom scales) in that symptom from baseline. The denominator will consist of a subset of the FAS who have a baseline symptom score  $\geq 10$ .

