**Table 17 Formal statistical analysis methods and pre-planned sensitivity analyses**

Endpoints analyzed	Notes
Time to symptom deterioration (EORTC QLQ-C30 endpoints)	Stratified log-rank test
Symptom improvement rate (EORTC QLQ-C30 endpoints)	Logistic regression
Change from baseline in symptoms (EORTC QLQ-C30 endpoints)	MMRM analysis

DoR Duration of response; EORTC QLQ-C30 European Organisation for Research and Treatment of Cancer 30-item core quality of life questionnaire; FAS Full analysis set; HR Hazard ratio; HRR homologous recombination repair; HRRm Homologous recombination repair mutant; KM Kaplan-Meier; MMRM Mixed effect model repeat measurement; ORR Objective response rate; OS Overall survival; OS18 Patients alive at 18 months; PD-L1 Programmed death ligand 1; PFS Progression-free survival; PFS6 Progression-free at 6 months; RECIST 1.1 Response Evaluation Criteria in Solid Tumors, version 1.1.

Prior to unblinding for the primary analysis, the proportion of patients in each stratification level will be reviewed, and levels may be combined or factors may be removed from the analyses, if the numbers are too small.

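### Section 9.4.2.7 applies the logistic regression to a best PRO response rate, Table 17 applies it to the confirmed symptom improvement rate, and the confirmed HRQoL/function rate is never analysed

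*Protocol*

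**What the plan says.** Section 9.4.1.3 defines two kinds of PRO response.

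- **Best response.** Each post-baseline visit is classed as improvement, no change or deterioration against a 10-point threshold (Table 16). The best overall response "will be derived as the best response the patient achieved, based on evaluable PRO data collected during the study period". No confirmation rule and no denominator are stated; the next sentence reads "Additional details will be provided in the SAP".
- **Improvement rates.** The symptom improvement rate counts "patients with 2 consecutive assessments at least 14 days apart that show a clinically meaningful improvement", among patients with a baseline symptom score of at least 10. The HRQoL/function improvement rate uses the same two-assessment rule, among patients with a baseline score of at most 90.

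Table 17, which lists the endpoints for formal analysis, gives logistic regression as the method for the symptom improvement rate. It has no row for an HRQoL/function rate.

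Section 9.4.2.7 treats the symptom improvement rate as descriptive: "A summary of the symptom improvement rate for each of the 3 symptom scales will be produced". For function and global health status/QoL it summarizes a best response rate. The regression is then assigned as follows: "The best symptom response rate and HRQoL/function response rate will be analyzed by comparing the treatment arms using a logistic regression model". An odds ratio, p-value and 95% CI go on a forest plot.

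**The concern.** Fatigue, pain, physical function and global health status/QoL are the PRO measures named in the secondary objectives. For the two symptom scales, Table 17 and Section 9.4.2.7 name different variables for the same test. For function and QoL, the confirmed variable is defined and then dropped.

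The choice affects the result. A best-ever response needs one favourable visit out of all those completed, so random fluctuation in questionnaire scores creates responders. Requiring two consecutive improved visits removes many of them. Chance responders occur in both arms and pull the odds ratio towards 1. If the conflict is still open when data are seen, either variable can be defended as pre-specified.

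**Working it through.** The protocol gives no expected responder rate, within-patient SD or power for this analysis, so there is no stated figure to reproduce.

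**Step 1: passages side by side**

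| Place | Symptom scales | Function and global QoL |
|---|---|---|
| 9.4.1.3, improvement rates | Confirmed; baseline ≥10 | Confirmed; baseline ≤90 |
| 9.4.1.3, best response | No confirmation or denominator stated | Same |
| Table 17, logistic regression | Improvement rate | Not listed |
| 9.4.2.7, summary | Improvement rate | Best response rate |
| 9.4.2.7, logistic regression | Best response rate | Response rate |

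**Step 2: chance responders under each rule**

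From the protocol: the 10-point threshold, the two-consecutive-visit rule, questionnaires every 4 weeks on treatment (Table 1) and 75 patients per arm (Section 9.2). Assumed: independent normal noise with SD s at baseline and at each of K completed visits, and a constant true score.

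At a single visit, P(improvement ≥10) = 1 − Φ(10/(s√2)). For s = 10 this is 1 − Φ(0.707) = 24%. Over K visits all comparisons share the same noisy baseline, so the rates were simulated (400,000 patients per cell). Each cell shows best single visit v two consecutive visits.

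| s | K = 3 | K = 6 | K = 8 |
|---|---|---|---|
| 5 | 18% v 4% | 27% v 7% | 31% v 9% |
| 7.5 | 35% v 10% | 48% v 18% | 53% v 21% |
| 10 | 45% v 16% | 59% v 26% | 64% v 31% |
| 12.5 | 51% v 20% | 65% v 32% | 70% v 37% |
| 15 | 56% v 23% | 69% v 36% | 74% v 42% |

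The ratio runs from about 5 (s = 5, K = 3; 17.5/3.5 before rounding) down to 74/42 = 1.8.

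On a bounded, stepped two- or three-item scale (assumed mean 35, SD 22; s = 7.5 to 15; K = 6), with baseline ≥10 required under both rules, the rates are 58% to 82% against 29% to 51%. At K = 8 and s = 15 on the three-item scale they are 86% v 57%, a ratio of 1.5. A low-scoring two-item scale (assumed mean 8, SD 15) narrows this further, to 94% v 71%, a ratio of 1.3. If scores worsen by 2 points per visit (K = 6), the unconfirmed rate is 24% at s = 7.5 and 55% at s = 15, against 6% and 24%.

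**Step 3: dilution**

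Suppose 20% of control and 40% of combination patients have a sustained 20-point gain, with K = 6, s = 10 and all 75 per arm evaluable. The odds ratio for true gain is (0.40/0.60)/(0.20/0.80) = 2.67.

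- Confirmed rule: 38.2% v 50.4%, odds ratio (0.504/0.496)/(0.382/0.618) = 1.64, power about 32%.
- Best single visit: 66.1% v 74.2%, odds ratio (0.742/0.258)/(0.661/0.339) = 1.47, power about 19%.

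**Step 4: time on treatment**

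The stepped fatigue scale was simulated with no symptom effect, three post-treatment visits, and treatment time following the planning medians: 3 months, and 3/0.55 = 5.45 months. At s = 8 the best-visit rates are 69.2% v 73.2%, odds ratio (0.732/0.268)/(0.692/0.308) = 1.22. The confirmed rates are 38.2% v 42.9%, odds ratio (0.429/0.571)/(0.382/0.618) = 1.22. Confirmation does not remove this imbalance.

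**The case against.** The strongest reply is that this is loose terminology. The term best symptom response rate is defined nowhere. The best overall response in Section 9.4.1.3 is a category, not a rate, and is not tied to the regression. The only PRO rates defined are the confirmed ones, Table 17 points to the confirmed symptom rate, and the summary sentences in Section 9.4.2.7 move between the two terms as if they were equivalent. The best-response details are also left to the SAP, so the absence of a confirmation rule in the protocol does not show that none will apply.

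Much of this stands. The link from the regression sentence to the unconfirmed derivation is the natural reading, not an explicit statement. It does not remove the conflict, because a SAP that follows Table 17 departs from the wording of Section 9.4.2.7 and the reverse. If the terms were meant as synonyms, the same edit is needed to say so.

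The consequence is also limited. Only PFS and OS are in the testing sequence (Sections 9.1 and 9.4.10), and the same instrument is analysed by time to deterioration and a repeated-measures model. The stepped-scale figures cover symptom scales only. Global QoL rests on two seven-point questions, so one category on one question moves the score by 100/12 = 8.3, below the threshold.

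**Conclusion.** The contradiction holds on the text: two variables, with different confirmation rules and denominators, are named for one formal comparison, and the confirmed HRQoL/function improvement rate is analysed nowhere. Taken literally, Section 9.4.2.7 tests an unconfirmed variable with roughly 1.5 to 5 times as many chance responders as the confirmed rate. That factor rests on assumed noise of 5 to 15 points and 3 to 8 completed visits, and can be smaller on a scale with very low scores.

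Two stronger readings are not supported. A reader might infer that noise makes most patients responders. The protocol gives no variability figure, and the result depends on it: 18% to 31% at an SD of 5, and 31% to 47% for SDs of 7.5 to 15 if only on-treatment visits at a 3-month median are counted. A reader might also infer that confirmation would stop the odds ratio from reflecting time on treatment. The null odds ratio is about 1.22 under both rules, so this is not a reason for the change.

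**What to change.** In Section 9.4.2.7, name the symptom improvement rate and the HRQoL/function improvement rate of Section 9.4.1.3 as the variables both summarized and compared by logistic regression. State the rule (two consecutive assessments at least 14 days apart) and the denominators (baseline symptom score ≥10; baseline function or QoL score ≤90). Add the HRQoL/function improvement rate to Table 17, which has no such row. The best overall response in Section 9.4.1.3 may stay as a descriptive summary, labelled as unconfirmed.

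The cost is a wording change in the protocol, carried into the SAP, with no new data collection. Reported improvement rates will be lower than under a best-visit rule.
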